4.2 Selection of Study Population

4.2.1 Number of Planned Subjects

Approximately 90 subjects are planned to be randomized to receive treatment with Restylane Skinboosters Vital Lidocaine in the right hand, and Restylane Vital in the left hand, or vice versa. Refer to Section 7 for the statistical considerations on which the sample size is based.

4.2.2 Inclusion Criteria

Refer to Section 5.2.1 of the study protocol.

4.2.3 Exclusion Criteria

Refer to Section 5.2.2 of the study protocol.

 EST. 1981	Title 43CH2305 Statistical Analysis Plan	Doc id MA-59378
---	--	---------------------------

Study Number 43CH2305
Statistical Analysis Plan

CONFIDENTIAL

Page 14 of 36
Final, 1.0, date 24APR2024

4.2.4 Method of Assigning Subjects to Treatment Groups

Upon signature of the Informed Consent Form (ICF), each subject will be assigned a screening number consisting of "S" and the site number followed by a consecutive number starting with 01 at each site, e.g., S101, S102. The screening number shall be listed on a subject screening and inclusion log.

Each subject will be assigned a subject number as they arrive for the treatment visit. Randomization will be assigned via the eCRF system. The subject number is also the randomization number and will ensure the assignment of Restylane Skinboosters Vital Lidocaine in the right hand, and Restylane Vital in the left hand, or vice versa, is random. The treatment information will be kept by the Treating Investigator during the study not to be disclosed to the subjects. Refer to Section 4.1.1 for an illustration of the study design and treatment allocation.

4.2.5 Allocation Concealment and Blinding

Only the subject will be blinded. Treating Investigator will not be blinded to the treatment assignment.

The Treating Investigator is not allowed to discuss treatment assignment per hand with the subjects. All documents with information on study products shall be kept in a separate binder not available to the subjects.

To ensure the subject is kept treatment-blind the following measures are to be employed at the study site when injecting: the same injection techniques, volume per injection point and similar total volume should be used for both hands.

At the discretion of the investigator, the subject can listen to white noise/music in headphones during the treatment to cancel out the click sounds from the syringe when injecting Restylane Vital Skinboosters Lidocaine.

The injection will be performed behind a screen to prevent the subject from seeing the type of syringe used.

5 PLANNED ANALYSES

5.1 Interim Analyses

Not applicable.

5.2 Final Analyses

The final analyses, including all data collected in the study, will be performed after database lock.

	Title 43CH2305 Statistical Analysis Plan	Doc id MA-59378
--	--	---------------------------

Study Number 43CH2305
Statistical Analysis Plan

CONFIDENTIAL

Page 15 of 36
Final, 1.0, date 24APR2024

6 ANALYSIS SETS

6.1 Full Analysis Set

The Full Analysis Set (FAS) includes all subjects who were treated with Restylane Skinboosters Vital Lidocaine in one hand and Restylane Vital in the other hand. Subjects are analyzed according to the randomization assignment.

The FAS is the primary set for all effectiveness analyses.

6.2 Per Protocol Analysis Set

The Per Protocol Analysis Set (PPS) includes all subjects in FAS that comply to the protocol procedures with no deviations considered to have a substantial impact on the evaluation of the primary endpoint.

For this study, the following protocol deviations that will exclude subjects from PPS are identified (but not limited to):

- VAS assessment at end of injection missing for at least one side,
- Study products not administered according to randomization,
- Any topical or local anesthetic or other pain-relieving medication used before all VAS assessments are completed,
- Significantly different injection volumes in left and right hand.

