#### 5.2.2 Exclusion Criteria

1. Any previous non-permanent or permanent implant/filler in the hands, including autologous fat
2. Any mesotherapy or resurfacing procedure (laser, chemical peels or other ablative or non-ablative treatment) in the hands within 6 months prior to baseline
3. Any previous hand surgery including sclerotherapy
4. Any fibrosis or scarring or deformities on the hands
5. Advanced photoaged/ photodamaged skin (e.g. advanced skin elastosis, multiple lentigo solaris lesions) or skin condition with very crinkled or fragile skin on the dorsal hands
6. Subjects with active skin disease, inflammation or related conditions in the hand
7. Subjects with a history of precancerous (e.g. actinic keratosis) or cancerous lesions in the hands
8. Subjects with a history of Raynaud's disease or phenomenon, or history of other disease that may affect peripheral circulation
9. History of neurological disease that may affect peripheral neurological function
10. Subjects with a history of autoimmune disease or joint disease or connective tissue disease (e.g. rheumatoid arthritis, lupus, scleroderma etc)
11. Subjects with known hypersensitivity to any ingredient of the study product or anesthesia used in the study or with a history of any significant Adverse Events caused by dermal fillers
12. Use of topical retinoids on the dorsal hands within 6 weeks prior to baseline or use of systemic retinoids within 6 months prior to baseline
13. History of chronic lymphedema or breast cancer / mastectomy with potential to cause edema
14. Concomitant thrombolytic or anticoagulant therapy and therapy with inhibitors of platelet aggregation, (e.g. non-steroid anti-inflammatory drugs, acetylsalicylic acid, Omega 3 and Vitamin E) within 2 weeks prior to treatment, or a history of bleeding disorders. Cyclooxygenase-2 (COX-2) inhibitors are allowed
15. Treatment with chemotherapy, immunosuppressive agents, immunomodulatory therapy (e.g. monoclonal antibodies), systemic or topical (dorsal hands) corticosteroids (inhaled corticoids are allowed) within three months before study treatment
16. History of untreated epilepsy or other significant medical conditions

 EST. 1981	Title 43CH2305 CSP Vital-Lido-Hand-2w	Doc id MA-57336
---	---	---------------------------

17. Women who are pregnant or breast feeding, or Woman of childbearing potential who are not practicing adequate contraception or planning to become pregnant during the study period.

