4 INVESTIGATIONAL PLAN

4.1 Overall Study Design and Plan

This is a randomized, multi-center, split-hand, subject-blinded study comparing pain, safety and effectiveness of Restylane Skinboosters Vital Lidocaine and Restylane Vital without lidocaine for improving appearance of the dorsal hands in Chinese subjects.

Written informed consent will be obtained before any study related procedure is performed. Subjects will be screened for eligibility within 14 days prior to study randomization on Day 1. The Screening Visit and Baseline Visit can be performed on the same day.

GALDERMA <small>EST. 1981</small>	Title 43CH2305 Statistical Analysis Plan	Doc id MA-59378
---	---	----------------------------------

Study Number 43CH2305
Statistical Analysis Plan

CONFIDENTIAL

Page 11 of 36
Final, 1.0, date 24APR2024

Each subject will receive treatment on Day 1 with Restylane Skinboosters Vital Lidocaine® in one hand and Restylane Vital in the opposite hand, as randomly assigned. Study treatment will be unblinded for the Treating Investigator. The first injection will always start in the right hand. No topical or local anesthetic or other pain-relieving medication should be used before all VAS assessments are completed. Ice for pain relief is allowed and should be applied equally on both hands before treatment, and an approximately two-minute ice application time per hand is recommended. Ice may also be used after all VAS evaluations have been completed. The second treatment, that is the injections in the left hand, will be performed after the treatment of the first (right) hand and the VAS assessment at T0 of the right hand is completed.

The subject will assess pain experienced directly after treatment on a 100 mm VAS at the end of each treatment (before massaging the treatment area). The time should be recorded in the electronic Case Report Form (eCRF) and the pain will thereafter be assessed by the subject at 10 ± 3 , 20 ± 3 , and 30 ± 3 minutes on the VAS after the treatment on the right and left hand, respectively.

[figure not shown]
After the treatment of each hand is finished, and after the T0 pain assessment is complete, massage can be performed on the treated area of that hand. It is recommended not to exceed five minutes of massage to avoid affecting subsequent VAS assessments. It is not necessary to massage both hands simultaneously.

[figure not shown]
A safety follow-up telephone call should be made 72 hours after treatment.

CCI

CCI

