8 EFFECTIVENESS, SAFETY AND OTHER ASSESSMENTS

8.1 Effectiveness Assessments

8.1.1 Pain assessment by Visual Analogue Scale (VAS)

The VAS is a subjective scale to measure pain intensity (Appendix 12.1). The subject shall be instructed to put a vertical mark, approximating the pain experienced after the procedure, on a 100 mm horizontal line labelled “no pain” at the left end and “the worst pain you can imagine” at the right end. The distance in mm from the left end (no pain) to the subject’s VAS mark shall be measured with a standard ruler. Each hand will be evaluated independently.

Subjects will evaluate injection site pain for each hand at the time of injection completion (before massaging) and at 10, 20, and 30 minutes post-treatment by completing a VAS.

CCI

[REDACTED]

GALDERMA <small>EST. 1981</small>	Title 43CH2305 Statistical Analysis Plan	Doc id MA-59378
---	--	---------------------------

2024-04-25 10:28

Effective date:

Effective

Version: 1.0

Study Number 43CH2305
Statistical Analysis Plan

CONFIDENTIAL

Page 17 of 36
Final, 1.0, date 24APR2024

CCI

CCI

CCI

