9.1 Effectiveness Endpoints

9.1.1 Primary Effectiveness Endpoint

The primary effectiveness endpoint is the within-subject difference in VAS score at the end of injection (T0), and will be calculated as:

- $\Delta_{T0} = (\text{VAS score at T0 for the Restylane Skinboosters Vital Lidocaine hand}) - (\text{VAS score at T0 for the Restylane Vital hand})$.

CCI

2024-04-25 10:28

Effective date:

Effective

Version: 1.0

Study Number 43CH2305
Statistical Analysis Plan**CONFIDENTIAL****Page 20 of 36**
Final, 1.0, date 24APR2024

CCI

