10.4.3 Sensitivity Analysis of Primary Endpoints

To investigate the assumptions underlying the model, analysis of the distribution of the within-subject differences will be done. If the distribution of the differences seems to be deviating from normal, a Wilcoxon signed-rank test will be used as a sensitivity analysis. However, the statistical hypotheses to be tested will change from the one specified in Section 3.3.1 to the following:

 EST. 1981	Title 43CH2305 Statistical Analysis Plan	Doc id MA-59378
---	--	---------------------------

Study Number 43CH2305
Statistical Analysis Plan

CONFIDENTIAL

Page 28 of 36
Final, 1.0, date 24APR2024

$$\begin{cases} H_0: \tilde{\Delta} \geq 0 \text{ mm} \\ H_1: \tilde{\Delta} < 0 \text{ mm,} \end{cases}$$

[figure not shown]
where $\tilde{\Delta}$ denotes the median within-subject difference in VAS score (Restylane Skinboosters Vital Lidocaine - Restylane Vital) at the end of injection.

To assess the robustness of the primary effectiveness results, the following sensitivity analyses will be conducted:

1. Observed Case (OC) analysis of the within-subject difference in VAS score at T0 on the FAS under Missing Completely at Random assumption,
2. Analysis of the within-subject difference in VAS score at T0 will be repeated on the PPS.

The analyses in 1) and 2) will follow the outline in Section 10.4.2, however, no analyses by study site will be done. If the normality assumption is found to be questionable, 1) and 2) will also be performed using the Wilcoxon signed-rank test.

CCI

	Title 43CH2305 Statistical Analysis Plan	Doc id MA-59378
--	--	---------------------------

Study Number 43CH2305
Statistical Analysis Plan

CONFIDENTIAL

Page 29 of 36
Final, 1.0, date 24APR2024

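### The per protocol set drops subjects for pain relief taken after the left-hand T0, when the T0 primary endpoint is already complete

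*SAP*

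**What the plan says.** **The set and its criterion.** SAP 6.2 defines the PPS as FAS subjects who followed the protocol with "no deviations considered to have a substantial impact on the evaluation of the primary endpoint". It then lists deviations that will exclude a subject, one of them being "Any topical or local anesthetic or other pain-relieving medication used before all VAS assessments are completed". Protocol 6.3 carries the same criterion.

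**The VAS schedule.** SAP 8.1.1 has each hand scored "at the time of injection completion (before massaging) and at 10, 20, and 30 minutes post-treatment by completing a VAS".

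**The endpoint.** SAP 9.1.1 computes the primary endpoint from the two T0 scores only, lidocaine hand minus comparator hand.

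**The order of the hands.** SAP 4.1 has the left-hand injections "performed after the treatment of the first (right) hand and the VAS assessment at T0 of the right hand is completed".

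**The use of the set.** SAP 10.4.3 names two numbered robustness analyses of the primary result. The second is: "Analysis of the within-subject difference in VAS score at T0 will be repeated on the PPS". Protocol 6.5 gives the PP analysis a larger role, as the estimate of the true clinical effect of treatment. The FAS, which has no medication exclusion, is the primary set (SAP 6.1).

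**The concern.** The criterion is longer than the endpoint it protects. A subject who takes a pain reliever between the left-hand T0 and the left-hand T30 already has both T0 scores on paper. The medication cannot change them, but the subject is removed from the T0 analysis.

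That is an exclusion on an event after the outcome. At the least it discards valid data and contradicts the principle stated at the head of SAP 6.2. If those who seek relief differ in their between-hand difference, it also shifts the PPS estimate. A gap between FAS and PPS could then be put down to non-compliance when part of it comes from the set's definition.

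**Working it through.** **1. The plan's own figures.** With a mean difference of −10 mm, an SD of 25 mm and one-sided α of 0.025, the noncentral t distribution gives power 0.9016 at n = 68, so the stated 68 for 90% reproduces. Adding 15% gives 68 × 1.15 = 78.2 (about 80), and 80 / 0.90 = 88.9 (about 90). None of these depends on the PPS rule.

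**2. The timeline, from the text.**
- Right-hand injection, then right-hand T0.
- Left-hand injection, then left-hand T0. *The primary endpoint is complete here.*
- T10, T20 and T30 for each hand, the last being left-hand T30. *The criterion ends here.*

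Medication before the left-hand T0, including between the two T0 scores, can affect the endpoint and is rightly covered. Only the stretch from left-hand T0 to left-hand T30 is at fault. The visible T10–T30 summaries use the FAS (SAP 10.4.1.1), so in the readable text the longer window protects no PPS result.

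**3. Illustrative size.** From the documents: difference −10 mm, SD of the difference 25 mm. Assumed, because the documents give no values: comparator-hand T0 mean 45 mm, SD 25 mm per hand, and a fraction f of 5% or 10% dropped for medication after T0. The correlation then follows: ρ = 1 − 25² / (2 × 25²) = 0.5. Write V for the comparator hand, L for the lidocaine hand, and D = L − V.

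- *Use unrelated to pain:* no shift in the mean of D.
- *Use follows the two-hand average:* Cov(L − V, L + V) = Var(L) − Var(V) = 0 with equal SDs, so no shift.
- *Use follows comparator-hand pain (the highest f of V removed):* the slope of D on V is ρ − 1 = −0.5, so the shift is 0.5 × 25 × φ(z) / (1 − f), where z is the upper-f normal quantile.
  - f = 5%: 12.5 × 0.1031 / 0.95 = 1.36 mm, giving −8.64 mm.
  - f = 10%: 12.5 × 0.1755 / 0.90 = 2.44 mm, giving −7.56 mm.
  - Simulation of one million pairs agrees: −10.02 to −8.66 and −10.02 to −7.59.
- *Use follows the worse hand (the highest f of max(V, L) removed), by simulation:*
  - f = 5%: −9.95 to −9.31, a shift of 0.64 mm, so −9.36 from a true −10.
  - f = 10%: −10.02 to −8.96, a shift of 1.06 mm, so −8.94 from a true −10.

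These rules are deterministic. With noise of SD 25 mm added to the pain that drives use, the 10% means are −9.35 mm (worse hand) and −8.30 mm (comparator hand). At 2% use the deterministic means are −9.68 and −9.42 mm.

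The direction belongs to these two rules. Use driven only by lidocaine-hand pain would, by the same slope argument with the sign reversed (1 − ρ = +0.5), move the mean away from zero by the same amount as the comparator-hand rule. That is a less natural assumption if lidocaine works.

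**4. Against sampling error.** The standard error at 90 subjects is 25 / √90 = 2.64 mm. The 5% worse-hand shift is 0.64 / 2.64 = 0.24 of it; the 10% comparator-hand shift is 2.44 / 2.64 = 0.92 of it.

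**The case against.** The best reply is that this matters little. Pain-relieving medication is barred until all VAS scores are taken (Protocol 5.7.3.4), the window is about half an hour at the treatment visit, and the FAS carries the primary test. All of that stands. It limits the size of the problem but does not make the criterion fit its purpose, since the rule acts only when the deviation occurs.

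The longer window might serve PPS analyses of later timepoints in blacked-out text. That cannot be ruled out, but it would not justify applying the window to T0. Protocol 6.8 says deviating subjects might be excluded, which sounds like discretion; Protocol 6.3 and SAP 6.2 say the listed deviations will exclude.

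Two stronger readings are tempting and should not be drawn:
- *That the PPS estimate is biased toward zero as a matter of fact.* No passage says who takes relief or how often. High pain alone is not enough: use must depend on the worse hand, one particular hand or the difference. If it follows average pain, step 3 gives no shift.
- *That the criterion contradicts exclusion 14 of Protocol 5.2.2, where* "Cyclooxygenase-2 (COX-2) inhibitors are allowed". That is an eligibility rule on anticoagulant and platelet-inhibiting therapy before treatment. It gives no permission for pain relief during VAS scoring, and an eligible subject may later leave a per protocol set. At most, the start of the window is not spelled out.

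**Conclusion.** The mismatch is real and rests on the text alone: the criterion runs to the left-hand T30, the endpoint ends at the left-hand T0, and the set is defined by impact on that endpoint. The certain consequence is loss of valid T0 data, on a post-outcome event, from one sensitivity analysis.

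Bias is conditional. Under the assumptions in step 3, the range at 5–10% use runs from no shift to about 0.6–1.1 mm toward zero (worse-hand dependence) or 1.4–2.4 mm toward zero (comparator-hand dependence). The usage rate is assumed, and actual use should be low because it is barred.

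A reader might infer that the primary conclusion is at risk. It is not: the FAS test, its type I error and the sample size do not depend on this rule. The point matters for reading the PPS result, the more so because Protocol 6.5 presents it as the true clinical effect.

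**What to change.** In SAP 6.2 and Protocol 6.3, for the PPS analysis of the T0 endpoint, end the medication criterion at the second T0, for example: *used before the T0 VAS assessment of both hands is completed*. Keep listing later use as a protocol deviation. The clinical rule on pain relief stays as it is; only the definition of the analysis set changes.

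The cost is one line in each document plus a check on data capture. The T0 time is to be recorded in the eCRF (Protocol 5.1.1), but Protocol 5.7.4 asks for the name of a concomitant medication and the reason for it and does not mention clock time. Confirm that the eCRF shows whether a medication was taken before or after the left-hand T0, and add a time or a yes/no field if it does not. The primary analysis needs no change.

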6.3 Safety Analysis Set

The Safety Analysis Set (SAF) includes all subjects who were injected in at least one hand. Subjects are analyzed based on the as treated principle.

All safety analyses will be based on the SAF.

7 SAMPLE SIZE CONSIDERATION

Several studies have been performed comparing the same HA-filler product with and without the addition of lidocaine or other analgesics. In the study 43CH1504¹, comparing Restylane for treatment of nasolabial folds with and without Lidocaine in subjects with Chinese ethnicity, the observed within-subject difference in VAS score during injection was 33.0 mm with a standard deviation of 24.4 mm. In another study, in subjects with Chinese ethnicity, 43TW1628², comparing Restylane Perlane with and without Lidocaine, the mean within-subject difference in VAS score at injection was 32.0 mm with a standard deviation of 19.5 mm.

However, due to the many injection points in the treatment of the hands, it is believed that the within-subject difference in VAS score will be considerably less in this study than what was seen in the NLFs in the previous two studies referred to. Thus, assuming a true mean within-subject difference of -10 mm and a standard deviation of 25 mm, a significance level of 2.5% and using a one-sided one-sample t-test, inclusion of 68 subjects will give a power of 90% to reject the null hypothesis of > 0 mm within-subject difference. To ensure sufficient power in the event of the need of a non-parametric test for the primary analysis, approximately 15% more subjects will be added

 EST. 1981	Title 43CH2305 Statistical Analysis Plan	Doc id MA-59378
---	--	---------------------------

Study Number 43CH2305
Statistical Analysis Plan

CONFIDENTIAL

Page 16 of 36
Final, 1.0, date 24APR2024

to the 68 needed for the t-test. Hence, approximately 80 subjects will be needed for the primary analysis. In addition, a drop-out rate of 10% is assumed. Thus, approximately 90 subjects will need to be randomized in order to have at least 80 evaluable subjects for the statistical analysis.

7.1 Sample Size Re-Estimation

Not applicable.

8 EFFECTIVENESS, SAFETY AND OTHER ASSESSMENTS

8.1 Effectiveness Assessments

8.1.1 Pain assessment by Visual Analogue Scale (VAS)

The VAS is a subjective scale to measure pain intensity (Appendix 12.1). The subject shall be instructed to put a vertical mark, approximating the pain experienced after the procedure, on a 100 mm horizontal line labelled “no pain” at the left end and “the worst pain you can imagine” at the right end. The distance in mm from the left end (no pain) to the subject’s VAS mark shall be measured with a standard ruler. Each hand will be evaluated independently.

Subjects will evaluate injection site pain for each hand at the time of injection completion (before massaging) and at 10, 20, and 30 minutes post-treatment by completing a VAS.

CCI

[REDACTED]

GALDERMA <small>EST. 1981</small>	Title 43CH2305 Statistical Analysis Plan	Doc id MA-59378
---	--	---------------------------

2024-04-25 10:28

Effective date:

Effective

Version: 1.0

Study Number 43CH2305
Statistical Analysis Plan

CONFIDENTIAL

Page 17 of 36
Final, 1.0, date 24APR2024

CCI

CCI

CCI

8.3 Safety Assessments

8.3.1 Adverse Events Assessment

AEs are to be monitored throughout the course of the clinical study from the time the ICF has been signed. All AEs are to be reported on the AE form in the eCRF with complete information as required.

If AEs occur, the main concern shall be the safety of the subjects. At the time of the ICF signature, each subject must be provided with the name and phone number of clinical study site personnel for reporting AEs and medical emergencies.

At each post-enrollment visit, the Investigator (or sub-Investigator) will question the subject about AEs using an open non-persuasive question to elicit reporting of AEs, for example, "Have you noticed any change in your health since the last visit?" Additional questioning and examination will then be performed as appropriate.

CCI

 EST. 1981	Title 43CH2305 Statistical Analysis Plan	Doc id MA-59378
---	--	---------------------------

2024-04-25 10:28

Effective date:

Effective

Version: 1.0

Study Number 43CH2305
Statistical Analysis Plan
CONFIDENTIAL
Page 18 of 36
Final, 1.0, date 24APR2024

CCI

8.3.2.1 *Vital Signs Assessment*

Not applicable.

8.3.2.2 *Physical Findings Assessment*

Not applicable.

